#### **6.14 Infant DXA Scans**

Infants in the PrEP Comparison Component will undergo DXA scans of the whole body and lumbar spine at their Birth Visit and of the lumbar spine Week 26 postpartum. Scans will be performed according to standardized procedures described in the study-specific MOP. Scan images will be transferred electronically for centralized reading and results will be transmitted electronically from the central readers to the Data Management Center (DMC). The centralized readings of all scans will be made available to the study sites after the last scan has been read centrally. However, if an infant experiences a bone fracture subsequent to his or her scan, the result of his or her scan will be provided to the site as soon as available.

#### **6.15 Fetal Ultrasound**

If sonographic results from the current pregnancy are not available from medical records at the time of screening during the PK and PrEP Comparison Components, a fetal ultrasound scan will be performed to confirm (or used to re-calculate) gestational age at entry into the study. Scans should be performed during the 30-day study screening period, and results must be available at the time of enrollment.

Ultrasound scans may be performed at the study site or at off-site facilities. A result report that minimally documents the following must be obtained for filing in participant study charts and entry into eCRFs:

- Date of scan
- Number of fetuses
- Biometry measures for
  - If  $\leq$  14 weeks gestation:
    - Crown-rump length
  - If  $>$  14 weeks gestation:
    - Femur length, abdominal circumference, and either or both head circumference and biparietal diameter
- Calculated gestational age on the date of the scan or estimated date of delivery

## 6.16 Questionnaires and Computer-Assisted Self-Interview (CASI)

### 6.16.1 PK Component

During enrollment and at Study Exit of the PK Component, maternal participants will be queried on demographic and behavioral HIV risk characteristics; this information will be recorded on an eCRF. Items from the following domains will be included:

- Sociodemographic characteristics
  - Current living situation
  - Household composition
- HIV risk perception for mother and infant
- Sexual behaviors

### 6.16.2 PrEP Comparison Component

#### 6.16.2.1 COVID-19

Throughout follow-up of the PrEP Comparison Component, a COVID-19 questionnaire will be administered to maternal participants at select study visits (see [Appendices IIA](#) and [IIB](#) and [Section 6.2](#)). This questionnaire will cover topics such as the potential impact of COVID-19 on participants' life and study participation; this information will be recorded on an eCRF.

#### 6.16.2.2 CASI

During enrollment and follow-up of the PrEP Comparison Component, maternal participants will be queried on the contextual factors, that have been shown to impact differential uptake and sustained use of PrEP in prior trials. Items from the following domains will be programmed into the CASI:

- Sociodemographic characteristics
  - Current living situation
  - Household composition
  - Private space for product storage
- HIV risk perception for mother and infant
- HIV stigma
- PrEP stigma
- Sexual behaviors
- Substance use
- PrEP beliefs and PrEP readiness
- Future orientation and aspirations; self-efficacy
- Mental health and post-traumatic stress symptoms
- Disclosure to peers, family members, and partner(s) about PrEP use and participation in the study
- Gender-based violence (GBV)
- Partnership characteristics: partner's HIV status

## **6.17 Additional Considerations for Laboratory Procedures**

Each study site and laboratory involved in this study will comply with the DAIDS policy on Requirements for DAIDS Funded and/or Sponsored Laboratories in Clinical Trials Policy, which is available at:

<https://www.niaid.nih.gov/research/daids-clinical-research-laboratory-specimens-management>

### **6.17.1 Specimen Collection**

Specimens will be collected for this study as indicated in the Schedule of Evaluations and per detailed guidance provided in the Laboratory Processing Chart (LPC), which will be available on the IMPAACT web site: [www.impaactnetwork.org](http://www.impaactnetwork.org).

In accordance with U.S. National Institutes of Health (NIH) recommendations, adult blood collection will not exceed 10.5 mL/kg or 550 mL, whichever is smaller, over any eight-week period.

In accordance with U.S. National Institutes of Health (NIH) recommendations, pediatric blood collection will not exceed 5 mL/kg in a single day or 9.5 mL/kg in any eight-week period.

In the event that blood collection must be limited, available specimens should be prioritized for use in the following order: (1) HIV testing, (2) Creatinine, (3) Drug levels, (4) stored plasma.

### **6.17.2 Specimen Preparation, Testing, Storage, and Shipping**

All specimens collected for this study will be labeled, transported, processed, tested, stored and/or shipped in accordance with the DAIDS policy referenced in [Section 6.17.1](#), site and local laboratory SOPs, and the LPC. The frequency of specimen collection and testing will be directed by the Schedule of Evaluations and specifications for clinical management provided in [Section 8](#). The Laboratory Data Management System (LDMS) will be used to document specimen collection, testing, storage, and shipping as specified in LPC.

Safety tests will be conducted in real time at the site laboratories.

Dried blood spot samples will be shipped to regional laboratories for TVF-DP drug levels. Samples will be shipped at a frequency which permits a site to receive results by the next study visit for the PrEP Comparison participants.

Infant specimens for HIV nucleic acid testing for infant HIV diagnosis and maternal specimens for HIV testing must be tested in a VQA-certified laboratory. HIV antibody tests must be performed according to GCLP guidelines and the laboratory must participate in an appropriate external QA program.

Maternal and infant sample swabs for microbiome analyses will be stored and batch shipped for analysis. No data from these samples will be available to the sites during the study.

Maternal vaginal secretions samples for drug level may be obtained with a soft plastic aspirator without speculum placement or by another appropriate technique and can be collected by the participant or by a clinician. Samples will be stored and batch shipped for testing. Since target drug concentrations for vaginal samples have not been determined, real time testing and reporting of vaginal specimen results to the sites will not be done. No vaginal specimens will be collected if

contraindicated by a pregnancy complication such as placenta previa or premature rupture of membranes.

After all protocol-specified laboratory testing has been performed, residual maternal and infant specimens may be of interest for future research use. Maternal participants (or other authorized guardians if applicable) will be asked to provide written informed consent for future research use of these specimens, if permitted by site IRBs/ECs and other applicable review bodies.

Participants may choose to provide or to decline informed consent for future research use of residual specimens with no impact on other aspects of participation in the study. With permission, human genetic tests may be performed on these samples. The genetic testing may be used to help understand variability in enzymes responsible for tenofovir and emtricitabine disposition and drug response including, drug transporters, kinases, phosphotransferases, or enzymes involved in drug response.

### **6.17.3 Biohazard Containment**

As the transmission of HIV and other blood-borne pathogens can occur through contact with contaminated needles, blood, and blood products, appropriate blood and secretion precautions will be employed by all personnel in the drawing of blood and shipping and handling of all specimens for this study as currently recommended by the U.S. Centers for Disease Control and Prevention, NIH, and other applicable agencies. All specimens will be shipped using packaging that meets requirements specified by the International Air Transport Association Dangerous Goods Regulations for UN 3373, Biological Substance, Category B, and Packing Instruction 650. Culture isolates, if obtained in this study, are to be shipped as specified for UN 2814 Category A Infectious Substances.

## **7 SAFETY MONITORING, ASSESSMENT AND REPORTING**

### **7.1 Safety-Related Roles and Responsibilities**

Participant safety will be carefully assessed, monitored, and reported at multiple levels throughout this study. [Sections 7.1, 7.2, and 7.3](#) describe safety-related roles, responsibilities, and procedures for site investigators. The safety monitoring roles of the Clinical Management Committee (CMC) and the IMPAACT Study Monitoring Committee (SMC) are briefly referenced in [Section 7.1](#) and described in greater detail in [Section 9.3](#).

#### **7.1.1 Site Investigators**

Site investigators are responsible for continuous monitoring of all study participants and for alerting the CMC if unexpected concerns arise. Site investigators will record safety-related data on eCRFs as indicated in [Section 7.2](#) and complete expedited adverse event (EAE) reporting as indicated in [Section 7.3](#). Site investigators are also responsible for prompt reporting to their IRBs/ECs and other applicable review bodies of any unanticipated problems involving risks to participants or others.

#### **7.1.2 Clinical Management Committee (CMC)**

The following Protocol Team members comprise the CMC: Protocol Chair and Vice Chairs, Medical Officers, Pharmacologists, Statisticians, Epidemiologist, Data Managers, Laboratory Data Managers, Clinical Trial Specialists, at least one international Protocol Investigator, or their

designees. The CMC will provide guidance as needed to site investigators regarding all aspects of participant management, including but not limited to questions of participant eligibility and management of adverse events, study drug administration, and other concomitant medications. Refer to [Section 8](#) for more information on participant management.

On behalf of the full Protocol Team, the CMC will monitor participant safety through routine review of study data reports as described in [Section 9.3](#).

### **7.1.3 Study Monitoring Committee (SMC)**

An independent IMPAACT Study Monitoring Committee (SMC) will monitor participant safety through routine and as needed reviews of study data. Refer to [Section 9.3.3](#) for more information on the composition and role of the SMC in monitoring of this study.

## **7.2 Safety-Related Data and Pre-Existing Conditions Data Collection**

*Note: This section describes eCRF data recording for pre-existing conditions and adverse events. As part of this description, reference is made to severity grading and criteria for EAE reporting; refer to [Sections 7.3.3](#) and [7.3.2](#), respectively, for detailed information on these topics.*

The definition of the term adverse event provided in Version 2.0 of the Manual for Expedited Reporting of Adverse Events to DAIDS (DAIDS EAE Manual) will be used in this study. This definition will be applied to all maternal and infant participants, in both the PK Component and in the PrEP Comparison Component, beginning at the time of enrollment, regardless of subsequent administration of or exposure to study drug. Any untoward medical conditions (including abnormal laboratory test results, signs, symptoms, or diseases) identified prior to enrollment will be considered pre-existing conditions. Refer to [Section 4.4](#) for more information on defining the effective point of enrollment in the study.

Pre-existing conditions and adverse events will be entered into eCRFs as specified in [Sections 7.2.1](#) (for maternal participants) and [7.2.2](#) (for infants). Additionally, in the PrEP Comparison Component all reported social harms will likewise be documented on eCRFs as specified in [Section 13.6](#).

### **7.2.1 Safety-Related Data Collection for Maternal Participants**

#### ***Pre-Existing Conditions***

All pre-existing conditions identified among maternal participants during the 30 days prior to study entry will be recorded on maternal medical history eCRFs.

#### ***Adverse Events***

The following adverse events— inclusive of abnormal laboratory test results and clinical signs, symptoms, and diagnoses — will be entered into maternal adverse events eCRFs:

For the PK Component:

- All Grade 3 or higher adverse events

For the PrEP Comparison Component:

- All Grade 2 or higher adverse events

For both the PK Component and PrEP Comparison Component:

- All adverse events that lead to a change of study drug
- All complications and sequela of adverse pregnancy outcomes.
- All serious adverse events (SAEs) as defined in Version 2.0 of the Manual for Expedited Reporting of Adverse Events to DAIDS (DAIDS EAE Manual)

### ***Laboratory Test Results***

In addition to the recording specified above, the following laboratory test results will be entered into the relevant maternal laboratory eCRFs, regardless of whether the test was protocol-specified or ordered by the site investigator for clinical purposes:

For the PK Component:

- All Grade 3 or higher hemoglobin, white blood cell count, absolute neutrophil count, and platelet count results

For the PrEP Comparison Component:

- All Grade 2 or higher hemoglobin, white blood cell count, absolute neutrophil count, and platelet count results

For both the PK Component and PrEP Comparison Component:

- All HIV test results
- All creatinine and creatinine clearance results regardless of severity grade
- All Grade 2 or higher ALT results
- All results that lead to a discontinuation of study drug
- All results that are serious as defined in Version 2.0 of the DAIDS EAE Manual

## **7.2.2 Safety-Related Data Collection for Infants**

### ***Pre-Existing Conditions***

Given that infants in Group 1 of the PK Component, Cohort 1 and Cohort 2/Step 2 (specifically, infants of mothers who undergo the step change while pregnant) of the PrEP Comparison Component will be exposed to study drug *in utero*, all abnormal conditions identified during and after birth will be considered adverse events. No pre-existing conditions will be entered into eCRFs for infants.

### ***Adverse Events***

The following adverse events — inclusive of abnormal laboratory test results and clinical signs, symptoms, and diagnoses — will be entered into infant adverse events eCRFs:

For the PK Component:

- All Grade 3 or higher clinical signs, symptoms and diagnosis

For the PrEP Comparison Component:

- All Grade 2 or higher clinical signs, symptoms and diagnosis

For both the PK Component and PrEP Comparison Component:

- Suspected congenital anomalies
- All SAEs as defined in Version 2.0 of the DAIDS EAE Manual

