### **Laboratory Test Results**

In addition to the recording specified above, the following laboratory test results will be entered into the relevant infant laboratory eCRFs, regardless of whether the test was protocol-specified or ordered by the site investigator for clinical purposes:

- All HIV test results
- All creatinine results regardless of severity grade
- All results that are serious as defined in Version 2.0 of the DAIDS EAE Manual

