**Table 5: Primary Outcome Measures – PrEP Comparison Component**

Primary Outcome Measures – PrEP Comparison Component	
Objective	Outcome Measures
2.3.1	PrEP adherence: TDF-DP drug concentration level in Dried Blood Spots (DBS)
2.3.2	Maternal Adverse Events: 
 
Maternal Grade 3 or higher adverse events (signs, symptoms, labs, and diagnoses)
 
Maternal Grade 2 or higher chemistry abnormalities
 
 Adverse Pregnancy Outcomes: Composite outcome of 
 
Spontaneous abortion (occurring at <20 weeks gestation)
 
Stillbirth (occurring at ≥20 weeks gestation)
 
Preterm delivery (<37 completed weeks' gestation)
 
Small for gestational age (<10th percentile using INTERGROWTH-21st norms and ultrasound derived gestational age at delivery)
 
 Infant Safety: 
 
Infant death within the first 26 weeks of life
 
Infant Grade 3 or higher adverse events (signs, symptoms, labs, diagnoses) reported between birth and exit
 
Infant bone mineral content based on DXA scan of the whole body (WB-BMC) at birth and lumbar spine (LS-BMC) at birth and 26 weeks postpartum
 
Infant creatinine and CrCl rate at birth and 26 weeks postpartum
 
Infant length for age z-score at birth and exit
 

2.3.2	

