3.2 Primary Outcome Measure(s) for PrEP Comparison Component

PrEP adherence:

- TFV-DP drug concentration level in Dried Blood Spots (DBS)

Maternal Adverse Events:

- Maternal Grade 3 or higher adverse events (signs, symptoms, labs, and diagnoses)
- Maternal Grade 2 or higher chemistry abnormalities

Adverse Pregnancy Outcomes:

Composite outcome of

- Spontaneous abortion (occurring at <20 weeks gestation)
- Stillbirth (occurring at ≥ 20 weeks gestation)
- Preterm delivery (<37 completed weeks' gestation)
- Small for gestational age (<10th percentile using **INTERGROWTH-21st** norms and ultrasound derived gestational age at delivery)

Infant Safety:

Infant Adverse Events

- Infant death within the first 26 weeks of life
- Infant Grade 3 or higher adverse events (signs, symptoms, labs, diagnoses) reported between birth and 26 weeks postpartum

Infant Growth and Development

- Infant bone mineral content based on DXA scan of the whole body (WB-BMC) at birth and lumbar spine (LS-BMC) at birth and 26 weeks postpartum
- Infant creatinine and CrCl rate at birth and 26 weeks postpartum measured by Schwartz equation
- Infant length for age z-score at birth and 26 weeks postpartum

4 Definitions

Baseline

Maternal baseline is defined as the measurement on or closest to the study entry date, and infant baseline is defined as the measurement at birth. For the PrEP Comparison Component analyses characterizing the proportion with optimal adherence to PrEP among women in Cohort 2 who subsequently decide to initiate PrEP, baseline is defined as the date initiating PrEP.

Visit Windows for Analysis

All analyses summarizing or referring to data by visit week include a visit window around the applicable study visit week. For maternal antepartum study visit weeks 4, 8, and 12 the visit window is +/- 14 days. The visit window is +/- 21 days for antepartum visit weeks 24 and 36. The Labor and Delivery/Infant birth visit may occur as soon as possible after delivery through 21 days postpartum. The visit window is +/- 21 days for the maternal and infant 6- week postpartum, 14-week postpartum, and 26-week postpartum visits.

Analysis Sets

PK Component:

- **PK Adherence Set:** All maternal participants on PrEP, including those in Group 1 and those in Group 2

PrEP Comparison Component:

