6.3.4 Fourth Primary Estimand

Primary Objective 2: To assess the safety of FTC/TDF for PrEP during pregnancy and postpartum by comparing pregnancy outcomes and maternal and infant safety between cohorts.	
Estimand description	Incidence rate ratio of cumulative adverse events up to the age 26-week visit among PrEP exposed vs. PrEP unexposed infants
Treatment	
Infants exposed to the following maternal treatment in utero and/or through breastfeeding:
 
 1. Daily oral PrEP (200 mg FTC/ 300 mg TDF) throughout follow-up. 2. Enhanced adherence support, including SMS messaging and feedback of drug levels with tailored counseling. 3. Behavioral HIV risk reduction package
Target population	Analysis set
Infants born to women who are pregnant and HIV-uninfected, 16-24 years of age, with a confirmed singleton pregnancy of 32 weeks' gestation or less and who have access to a mobile phone and are able to receive and read SMS messages	Infant Safety Set: all enrolled infants
Variable(s)	Outcome measure(s)
Infant adverse events: 
 • Infant death within the first 26 weeks of life • Infant Grade 3 or higher adverse events reported between birth and the age 26-week visit. 	Outcome measures as defined by the variable (graded according to the NIAID DAIDS Table for Grading the Severity of Adult and Pediatric Adverse Events). The start of person-time for the PrEP-exposed group is birth for Cohort 1 and birth or Cohort 2/step 2 entry (whichever is later) for Cohort 2; The start of person-time for the PrEP unexposed group is birth (Cohort 2 participants only; person-time is censored when initiating PrEP for participants enrolled in Cohort 2/Step 2).
Handling of intercurrent events	Handling of missing data

 • Mother's failing to start PrEP (in Cohort 1 or Cohort 2/Step 2) (Treatment policy strategy) • Mother's discontinuation of PrEP (Treatment policy strategy) 	Participants who discontinue follow-up before the age 26-week visit will have their outcome determined based on data available until the time of discontinuation (i.e., a participant who discontinued follow-up without a prior AE is assumed not to have an AE had they been observed for the intended duration).
Population-level summary measure	Analysis approach

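### Protocol 7.2.2 contradicts itself, and the infant primary outcome, on whether Grade 3 or higher infant laboratory results must be entered in an eCRF

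*Protocol*

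**What the plan says.** **Outcome.** Protocol Table 5 lists, under infant safety, "Infant Grade 3 or higher adverse events (signs, symptoms, labs, diagnoses) reported between birth and exit". SAP 3.2 has "Infant Grade 3 or higher adverse events (signs, symptoms, labs, diagnoses) reported between birth and 26 weeks postpartum". The fourth primary estimand (SAP 6.3.4) uses "Infant Grade 3 or higher adverse events reported between birth and the age 26-week visit", without the parenthesis, and analyses it as a Poisson incidence rate ratio of PrEP-exposed to unexposed infants.

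**Infant adverse event eCRF (Protocol 7.2.2).** The lead-in describes the events to be entered as "inclusive of abnormal laboratory test results and clinical signs, symptoms, and diagnoses". The list that follows for the PrEP Comparison Component has three items: "All Grade 2 or higher clinical signs, symptoms and diagnosis", "Suspected congenital anomalies", and SAEs as defined in the DAIDS EAE Manual.

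**Infant laboratory eCRF (Protocol 7.2.2).** This is additional to the adverse event form and covers clinically ordered as well as scheduled tests. It takes all HIV results, "All creatinine results regardless of severity grade", and results that are serious under the same manual.

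**Maternal rule (Protocol 7.2.1).** For the same component, the maternal adverse event form takes "All Grade 2 or higher adverse events", with no limit to clinical events. The maternal laboratory form adds Grade 2 or higher haematology and ALT.

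**Monitoring.** Protocol 9.3.3 and SAP 2.5 call an ad hoc SMC review if more than 15% of liveborn infants have a Grade 3 or higher event, once 50 pregnancies have ended in live birth.

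**The concern.** A primary safety outcome should be collectable under the plan's own data rules. Here the outcome includes laboratory events, but the only graded item on the infant adverse event form is worded as clinical, and the laboratory form is limited to two named tests plus serious results. The lead-in points the other way. A site that follows the lead-in enters a non-serious Grade 3 bilirubin or haemoglobin result; a site that follows the list does not.

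Two uses depend on this count: the rate ratio in SAP 6.3.4 and the 15% SMC trigger. If results are left out, the trigger responds late and the rate ratio loses precision. If sites read the section differently, or if clinicians in this open-label, non-randomised study differ by exposure in when they write a diagnosis, the two groups may not be recorded alike.

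**Working it through.** No figure in the plan turns on this point, so the main check sets the collection rules against the schedules (Appendices IIC and IIE).

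| Grade 3+ infant result | When it arises | Adverse event form | Laboratory form | Clearly required? |
|---|---|---|---|---|
| Creatinine | Birth, Week 26, early discontinuation; all infants | Lead-in only | Yes, every grade | Yes, but counting rule not stated |
| Any serious result | Any test | Yes, as SAE | Yes | Yes |
| Abnormality written as a clinical diagnosis | Any test | Yes | Not needed | Yes |
| Non-serious CBC or lymphocyte subset | Scheduled visits after confirmed infant HIV infection | Lead-in only | No | No |
| Non-serious result for another analyte | Only if clinically ordered | Lead-in only | No | No |

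The last two rows are the gap. The first row shows a related omission: a creatinine value reaches the laboratory form, but neither document says how a Grade 3 or higher value there enters the event count.

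**Effect on the rate ratio.** Let s1 and s0 be the shares of qualifying events that are entered for exposed and unexposed infants. Then

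observed ratio = true ratio × (s1 / s0).

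If s1 = s0, the under-recording cancels and only precision is lost. If they differ, the bias can go in either direction.

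**Effect on the trigger.** Let m be the share of infants with an event whose only qualifying events go unrecorded. The trigger is met when the true proportion exceeds 15% / (1 − m). The documents give no value for m, so the values below are assumptions:

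- m = 5%: 15 / 0.95 = 15.8%
- m = 10%: 15 / 0.90 = 16.7%
- m = 20%: 15 / 0.80 = 18.8%
- m = 30%: 15 / 0.70 = 21.4%

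**Effect on power, for illustration.** The nearest figure in the plan is Protocol Table 10: 10% in Cohort 2 (n = 100) against 23% in Cohort 1 (n = 200), 80% power, alpha 0.05. To reproduce it:

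- pooled proportion = (10 + 46) / 300 = 0.1867
- null SE = √(0.1867 × 0.8133 × (1/100 + 1/200)) = 0.0477
- alternative SE = √(0.10 × 0.90/100 + 0.23 × 0.77/200) = 0.0423
- power = Φ((0.13 − 1.96 × 0.0477) / 0.0423) = Φ(0.863) = 80.6%, which agrees with the plan.

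Multiplying both proportions by (1 − m), with equal loss in each cohort:

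| Assumed m | Observed proportions | Power |
|---|---|---|
| 5% | 9.5% vs 21.9% | 77.9% |
| 10% | 9.0% vs 20.7% | 75.0% |
| 20% | 8.0% vs 18.4% | 68.4% |
| 30% | 7.0% vs 16.1% | 60.9% |

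Table 10 compares proportions, whereas SAP 6.3.4 compares rates, so this shows only the direction and rough scale of the lost precision. Because creatinine, serious and diagnosed events are already collected, m covers only what remains after those.

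**The case against.** The strongest reply is that the lead-in governs. It says laboratory results are included, and the laboratory form is expressly additional to the adverse event form, so a careful site would enter a Grade 3 laboratory event. On this reading a clarifying line is enough.

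Several facts also limit the reach. The only safety test scheduled for all infants is creatinine, and it is recorded at every grade. Section 8.1 requires every infant adverse event to be source documented with its severity, so missed results should be retrievable. Section 9.3.2 says the CMC's safety reports tabulate abnormal laboratory results. The recording rule is the same for both cohorts, and equal loss cancels in the rate ratio. Details of the trigger and of event coding sit in the SPDSMP and the AIP, which are not available here.

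Most of this stands, and it sets the size of the point. It does not remove the contradiction. The lead-in introduces a list, and that list confines the graded item to clinical events. The maternal section uses the same lead-in with an unrestricted item, so the infant wording reads as a narrower rule. CMC reports can tabulate only what has been entered.

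**Conclusion.** The point holds as a contradiction within Protocol 7.2.2, and between that section and the outcome in Table 5 and SAP 3.2. A non-serious Grade 3 or higher infant result for an analyte other than creatinine or HIV is not clearly required in any eCRF, and sites may differ in entering it. It should be corrected, but its practical reach is modest: clinically ordered tests, and the CBC and lymphocyte subsets in infants with confirmed HIV.

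A reader might infer more, and the documents do not support it:

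- **That such results are never captured.** The lead-in includes them, source records hold them, and those recorded as diagnoses or SAEs are entered.
- **That the laboratory part of the outcome is creatinine alone.** Serious results for any analyte are taken. What share of Grade 4 results counts as serious depends on the DAIDS manual and cannot be judged here.
- **That the infant event rate is understated by a known percentage.** No document gives the share, and the 5% to 30% range above is assumed.
- **That the comparison is biased by exposure.** That needs unequal recording between groups. It is possible in this design, but nothing in the documents shows it.

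**What to change.** In Protocol 7.2.2, add to the infant adverse event eCRF list for the PrEP Comparison Component all laboratory results of Grade 3 or higher, whether protocol-specified or clinically ordered. Tell the sites, and ask for back-entry from source documents where feasible.

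If data entry has closed, restate the outcome in SAP 3.2 and 6.3.4 as clinical signs, symptoms and diagnoses, SAEs, and graded creatinine, and report this as a narrowing of the Table 5 outcome.

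In either case, state in SAP 6.3.4 that Grade 3 or higher creatinine values on the laboratory eCRF count as events, and that an abnormality also entered on the adverse event form is counted once.

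The first route costs one eCRF line, a site notice and some retrospective source review. The second costs a SAP wording change and a narrower primary outcome. Neither needs new tests.
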